Development of An Exergame for Caregivers of Individuals With Alzheimer's Disease or Related Dementias

NCT03124550

Study Protocol and Statistical Analysis Plan

Upload Date: 09/07/2020

Document Date: 09/20/2019

Study Protocol and Statistical Analysis Plan

We conducted a 6-week mixed-methods study to evaluate caregivers' user experiences with Go&Grow and its impact on their well-being. Prior to recruitment, this study was approved by our institutional review board.

Procedure & Data Collection

Session 1

In the first meeting, participants completed the consent form, demographic survey, and a pretest survey. Participants then received the Fitbit Alta HR, a Fitbit training, and a paper guide on how to use the Fitbit. Participants were asked to wear the Fitbit for the following week to assess their baseline physical activity level.

Session 2 & Deployment Period

After one week of using the Fitbit, participants were trained on how to use Go&Grow. Caregivers were then asked to wear the Fitbit and use Go&Grow at least once every other day for 6 weeks. Automated system logs collected data regarding participants' use of Go&Grow, such as when users logged into Go&Grow, when a story was posted, viewed, liked, or replied. Participants were compensated with a \$5 Amazon gift card for completing the weekly survey each week.

Session 3

After six weeks of using Go&Grow, we conducted semi-structured interviews using the Data-Driven Retrospective Interviewing method. Before the Session 3 interview, we reviewed each caregiver's log data (e.g., number of days logging onto Go&Grow, and number of stories posted) to begin assessing their Go&Grow engagement; we probed identified data patterns in the interview to examine how and why participants used Go&Grow, game enjoyment, physical activity, motivation, and social connectedness. Finally, participants completed a posttest survey that was the same as the pretest given at baseline.

Analysis

Paired T-tests were conducted to examine whether caregivers' exercise self-efficacy and their management of distress scores changed significantly at posttest compared to the pretest.

Within-person (WP) relationships between time (week), steps, and social contact were tested. Multilevel modeling with the LMER package in R was used to determine whether participants increased in weekly average steps and weekly social contact over the 6-week intervention. We used the following model:

$$\text{Level 1: Outcome } ij = \beta_0j + \beta_1(\text{week}) ij + e_{ij}$$

$$\text{Level 2: } \beta_0j = \gamma_00 + u_{0j}$$

Weekly steps at level 1 were expressed as a wp intercept, week & wp error term. For level 2, wp intercept was expressed as a function of fixed intercept.

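### The plan names app-use logs as the basis for the data-driven interview and does not name each caregiver's weekly steps or social contact, which limits what the interviews can explain about the modelled outcomes

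*Combined protocol and SAP*

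**What the plan says.** Five statements in the combined protocol and SAP bear on this.

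- **What the logs hold** (Session 2 & Deployment Period): "Automated system logs collected data regarding participants' use of Go&Grow, such as when users logged into Go&Grow". The other examples given there are story activity: posting, viewing, liking and replying.
- **What is reviewed before the interview** (Session 3): "we reviewed each caregiver's log data (e.g., number of days logging onto Go&Grow, and number of stories posted". The stated purpose is "to begin assessing their Go&Grow engagement".
- **What the interview covers** (Session 3): "we probed identified data patterns in the interview to examine how and why participants used Go&Grow, game enjoyment, physical activity, motivation, and social connectedness".
- **What the models test** (Analysis): "whether participants increased in weekly average steps and weekly social contact over the 6-week intervention". The model text adds: "Weekly steps at level 1 were expressed as a wp intercept, week & wp error term".
- **Order of Session 3**: the posttest survey comes last, after the interview.

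The Fitbit is worn for a baseline week and then through the six weeks of app use. A weekly survey is mentioned, but its content is not described. The source of weekly social contact is not stated.

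**The concern.** The interview method is presented as data-driven, and its topics include physical activity and social connectedness. The data named as driving it concern use of the app. The series that would show a caregiver's activity or contact rising or falling are not named in the preparation, although they are what the models analyse.

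This matters because of the design. With no comparison group, a slope on week mixes any effect of Go&Grow with illness, care load, season and the effect of wearing a tracker. The study calls itself mixed-methods and sets out to evaluate impact on well-being as well as user experience. The qualitative arm is where reasons for change could come from. An interviewer who knows that a caregiver's steps fell sharply in one particular week can ask about that week. An interviewer who has seen only log-on days and story counts has to rely on a general question and on recall over six weeks.

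**Working it through.** No arithmetic bears on this point. The plan states no sample size, target effect, standard deviation or dropout rate, and it gives no figure to reproduce. The check is a comparison of the relevant text.

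**1. Data named for the interview against outcomes modelled.**

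| Series | Recorded in the study? | Modelled? | Named in the pre-interview review? |
|---|---|---|---|
| Go&Grow log-on days, stories posted | Yes, system logs | No | Yes, as examples |
| Weekly average steps | Yes, Fitbit (1 baseline week + 6 weeks = 7 weekly values) | Yes | Not named |
| Weekly social contact | Yes, source not stated (6 weekly values if recorded every week) | Yes | Not named; inside the reviewed logs only if it is derived from them |

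**2. How open the lists are.** Both the contents of the logs and the items reviewed are introduced as examples, so neither list is closed. Every example is a measure of app use, however, and so is the stated purpose of the review. The natural reading is that the review concerned engagement. The text is silent on steps and contact and does not exclude them.

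**3. What the model can say about individuals.** Level 1 is Outcome_ij = β0j + β1(week)_ij + e_ij, and Level 2 is β0j = γ00 + u0j. The intercept varies by person. The slope β1 carries no person index and has no Level 2 equation, so all caregivers share one week slope. There is also no group term. The model therefore estimates neither a caregiver's own trajectory nor a contrast with people who did not use Go&Grow. Reasons for an individual rise or fall have to come from elsewhere, and the interview is the only other component described that could supply them.

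**4. Whether the data could be in hand.** Steps accumulate from the baseline week to the end of the six weeks, so they exist before Session 3. For social contact this is an assumption: it holds if the weekly survey or the logs record it.

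**5. Order of Session 3.** The posttest supplies the exercise self-efficacy and distress-management scores for the paired t-tests, and it follows the interview. More pointed questions about changes in steps, asked just before those self-ratings, could influence them. Any change to the interview therefore has to deal with the order as well.

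**The case against.** The strongest case on the other side is that this is a gap in reporting and not a fault in the design. Much of that case stands.

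- A reader might infer that app logs were the sole input. The documents do not establish this. The lists are illustrative, and Fitbit or survey data may have been looked at without being mentioned.
- A reader might infer that the interviews are unable to explain changes in steps or contact, or that caregivers were never asked about them. The Session 3 text does not support this. Physical activity and social connectedness are listed topics, the interview is semi-structured, and a caregiver can mention illness or travel without a chart. The interview guide is not in the document. A disrupted week may also show as a gap in log-on days.
- A reader might count both modelled outcomes as absent from the reviewed data. For social contact this is not established, because its source is not given. If it were built from story views, likes and replies, it would lie within the logs.
- A reader might size the problem by how far unrelated events in a few weeks could move the week slope. That is a limit of a single-group slope and would be the same after the fix, which leaves the model and its data untouched. The documents also give no sample size or target effect against which to judge such a shift.
- User experience is the first stated aim, and a log-based interview serves it directly.
- Probing step changes just before the posttest could bias the self-efficacy and distress scores. This objection to the remedy is sound, and completing the posttest first answers it.

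What remains is that the plan names nothing beyond app-use data as the basis for probing, and does not say how the interview accounts are to be linked to the model results.

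**Conclusion.** The point holds as a limitation. The interview preparation, as described, rests on app-use logs reviewed for engagement. It does not name the caregiver's weekly steps or weekly social contact, which are the outcomes of the uncontrolled models and correspond to topics on the interview list. This weakens the interviews as an explanation of individual changes in those outcomes without removing that ability.

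No numerical size can be attached. The effect is on how well a slope can be interpreted. The estimate, its standard error and the paired t-tests are unaffected by the gap itself. The conclusion assumes that the text describes the preparation fairly, and that social contact is recorded somewhere retrievable before Session 3. If the team did review steps and contact, stating so would largely settle the matter. Interviews, however well prepared, would not stand in for a comparison group.

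**What to change.** In Session 3:

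1. Add to the pre-interview review a one-page chart per caregiver showing weekly average steps (baseline week plus weeks 1–6), weekly social contact (from whichever source records it, with that source named) and Go&Grow log-on days.
2. Ask each caregiver neutrally about the largest rise and the largest fall in steps and in contact, leaving open whether Go&Grow or something else was the reason.
3. Report the reasons beside the week slopes as interpretation only. Do not use them to drop weeks or caregivers from the models.
4. Have participants complete the posttest before this interview, so that the probing cannot influence the scores used in the paired t-tests.

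The document is written in the past tense, so the interviews may already be complete. In that case, state which data informed them and set each existing account beside that caregiver's step and contact trajectory in the report.

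The cost is a few minutes of preparation per caregiver, a slightly longer interview and a change in the order of Session 3. No new visits, measures or participants are needed.

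### Does the undefined social contact outcome call for a change to the multilevel analysis?

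*Combined protocol and SAP*

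**What the plan says.** Social contact is named twice, both times under Analysis in the combined protocol and SAP. One sentence reports that "Within-person (WP) relationships between time (week), steps, and social contact were tested". The next gives the purpose of the multilevel model: to determine "whether participants increased in weekly average steps and weekly social contact over the 6-week intervention". The level 1 equation is written for a generic outcome with a random intercept and a fixed effect of week. The text under it describes steps alone: "Weekly steps at level 1 were expressed as a wp intercept, week & wp error term".

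Session 2 & Deployment Period describes two data streams that run through the six weeks, besides the Fitbit. System logs record events "such as when users logged into Go&Grow, when a story was posted, viewed, liked, or replied". A survey appears only through its payment, a gift card "for completing the weekly survey each week"; its content is not described. Session 3 lists "game enjoyment, physical activity, motivation, and social connectedness" among the interview topics.

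**The concern.** Steps can be traced to the Fitbit without much thought. Social contact cannot be traced to anything with certainty. If it is a count of actions in the app, it measures interaction inside the intervention and may move only because people opened the app more or less often. If it is a survey answer, it may cover contact with other people in general. These are different statements about caregivers' well-being.

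The scale matters too. A rating suits a linear model with a normal error more readily than a small count does. A week without a login could be scored zero, while a week without a survey would be missing. Two analysts working only from this text could therefore build different variables. If several were tried and one kept, the chance of a false positive would rise. Finally, the sentence on within-person relationships can be read as including an association between steps and contact, for which no model is given.

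**Working it through.** There is no stated figure to reproduce: the document gives no sample size, significance level, standard deviation or effect size. The check is mainly a reading of the text.

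**Which collections could give a weekly value?**

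| Collection | Occasions | Can supply weekly social contact? |
|---|---|---|
| Demographic survey | once | no |
| Pretest and posttest survey | two | no |
| Session 3 interview | once, qualitative | no |
| Fitbit | continuous | steps; nothing links it to contact |
| System logs | continuous | possible |
| Weekly survey | weekly | possible |

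Two sources remain. Counting "when a story was posted, viewed, liked, or replied" as four separate candidates, and adding the survey, gives five, but that splits one source into four.

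**Are the two evenly balanced?** No. Session 2 presents the logs as data on use of the app, and Session 3 says they were reviewed to assess engagement with it. The outcome is described as weekly, and only one instrument carries that word. This does not prove that the survey is the source, but it makes it the more natural reading. The step from weekly survey to weekly contact is the same kind of inference as the step from wearing a Fitbit to weekly average steps, which no sentence states either.

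**Choice among candidates.** Assume a two-sided 5% level, no true trend, independent candidates, and a measure chosen after seeing the results. The chance of at least one significant increase among k candidates is 1 − 0.975^k:

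- k = 1: 2.5%
- k = 2: 1 − 0.975² = 1 − 0.9506 = 4.9%
- k = 5: 1 − 0.975⁵ = 1 − 0.881 = 11.9%

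Simulation with an assumed 20 participants and six complete weeks gives 4.5% and 3.8% for k = 2 at correlations of 0.5 and 0.8, and 8.9% and 6.4% for k = 5. With the two sources actually described, the rise is from 2.5% to between 3.8% and 4.9%. If the measure was fixed beforehand, the figure is 2.5% and there is no inflation.

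**Drift in app use.** Participants were asked to "use Go&Grow at least once every other day for 6 weeks". The minimum is 7/2 = 3.5 use-days a week and daily use is 7. At an assumed one interaction per use-day, a log count moving from 3.5 to 7 between weeks 1 and 6 doubles, with slope (7 − 3.5)/5 = 0.70 a week; the reverse halves it. This needs the log source, exactly one interaction per use-day, and a move from one end of the range to the other. The text establishes none of these, so the figure illustrates a possibility and does not measure a fault in the plan.

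**The model.** The equation is written for any outcome. It accepts social contact from either source without alteration. Whether a count model would be preferable depends on the log source being the one used, which is not established.

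**The case for a change.** The strongest case for acting is that this is one of only two multilevel outcomes, that nothing in the text settles its source, and that two or three sentences would settle it without new data. Redaction does not explain the silence. A reader who wants to reproduce or interpret the contact trend cannot do so from this document, and if the logs were used, the result describes engagement with the app and not contact in general. All of that stands.

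The further step, that the analysis needs changing, does not follow. Writing down a definition the authors already hold alters no estimate, test or model. Sparse measurement detail is also not peculiar to this outcome: exercise self-efficacy and distress management, the two paired t-test outcomes, have no named instrument or scoring either, and no outcome is designated primary. Relabelling the variable as in-app interaction, reporting use-days beside it or fitting a count model would be sensible only if the logs were confirmed as the source. Narrowing the sentence on within-person relationships could do harm, because it reports in the past tense what was tested. If a steps–contact association was examined, narrower wording would hide it.

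**Conclusion.** The omission is genuine: one of two trend outcomes has no written source, scale or weekly scoring. It is missing detail in a brief retrospective summary, which those who ran the study can fill from what they did, and it gives no ground to alter the analysis. The multiplicity and app-use figures should carry no weight, since each depends on conditions that the document does not indicate.

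This rests on two assumptions: that the authors used a single measure fixed before they saw the results, and that this measure yields one value per week. The survey is the likelier source, but that is an inference, because its content is not given. If the source proves to be the logs, the contact trend should be read as interaction within Go&Grow; that limits interpretation but does not invalidate the model. Whether an association between steps and contact was also tested is a question for the authors, and the sentence is best left as it stands until they answer.

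### Does the plan promise a steps–social contact analysis that its only multilevel model cannot deliver?

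*Combined protocol and SAP*

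**What the plan says.** Three statements in the Analysis section bear on this.

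- **Scope.** The paragraph begins "Within-person (WP) relationships between time (week), steps, and social contact were tested".
- **Aim.** The next sentence says that multilevel modelling served to find out "whether participants increased in weekly average steps and weekly social contact over the 6-week intervention".
- **Model.** "We used the following model" introduces one two-level equation. A generic outcome for caregiver *j* in week *i* is an intercept plus a week term plus error. The intercept is a fixed mean plus a caregiver-specific deviation. The text below the equations restates this: "Weekly steps at level 1 were expressed as a wp intercept, week & wp error term" and "For level 2, wp intercept was expressed as a function of fixed intercept".

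The only other quantitative tests are paired t-tests on exercise self-efficacy and distress management, which involve neither steps nor social contact.

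**The concern.** Taken alone, the scope sentence names three variables and says that the relationships between them were tested. Three variables form three pairs: week with steps, week with contact, and steps with contact. The printed model can serve the first two. It has no term for the third, because neither steps nor contact appears on the right-hand side and no joint model of the two outcomes is given.

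Interpretation would be at stake. If both week slopes were positive, a reader relying on the scope sentence might conclude that caregivers who walked more in a given week also had more social contact in that week. Two separate time trends can neither support nor refute that. The text below the equations adds to the doubt, since it names only weekly steps as an outcome and leaves the contact model implicit.

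**Working it through.** The plan states no sample size, effect size or variance, so it has no figure to reproduce. The check sets the sentences against the terms of the model.

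**1. What the model estimates.** For a given outcome:

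- Level 1: Outcome_ij = β_0j + β_1·week_ij + e_ij
- Level 2: β_0j = γ_00 + u_0j

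Substituting gives Outcome_ij = γ_00 + β_1·week_ij + u_0j + e_ij. The fixed parameters are a mean and a week slope. Fitted once to steps and once to contact, the model yields two week slopes and no steps–contact parameter. The observation behind the concern is correct.

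**2. What the stated aim requires.** The aim asks whether each of two outcomes increased over the 6 weeks. That needs one week slope per outcome, so two slopes. The model supplies two, and the aim is fully covered.

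**3. Whether the within-person label fits the week model.** Week varies within a caregiver. If every caregiver contributes all 6 weeks (an assumption), mean week is the same for everyone and β_1 contains no between-person component. The label in the scope sentence therefore fits a time trend and does not in itself point to a steps–contact analysis.

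**4. Whether anything else in the plan calls for the third pair.** The procedures for Sessions 1 to 3 describe the baseline week, system logs, weekly survey, interview and posttest. None of them, and nothing else in the Analysis section, states a steps–contact hypothesis or conclusion. The paired t-tests concern other measures.

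**5. Whether the contact model is really missing.** The equation is written for a generic outcome, and the aim names both outcomes. An analyst would fit the equation to each. That the text below it mentions steps alone is a clerical shortening.

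**6. Effect of each reading on the results.**

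| Reading of the scope sentence | Week slope, steps | Week slope, contact | Paired t-tests |
|---|---|---|---|
| Time with each outcome | as specified | as specified | as specified |
| All three pairs | as specified | as specified | as specified |

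The broad reading would add an analysis. It would not alter any that is specified.

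**The case for a change.** The strongest case for a change is that the text should match the model under either reading and that the repair is cheap: narrow one sentence, or add an exploratory model of contact on week, person-mean-centred steps and person-mean steps, with a random intercept. The same two week slopes are compatible with any week-adjusted within-person correlation from −1 to +1, so the specified analysis says nothing about the third pair.

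The factual part stands: the sentence is broader than the model, and no steps–contact inference can be drawn from the two slopes. The rest carries less weight. That two separate regressions leave the correlation of their residuals undetermined is true by construction. It describes an analysis not done and does not measure an error in those that were.

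The added model would also need choices the plan does not make. It does not say which variable is the outcome, and it does not describe how contact was measured or on what scale, so the fit of a linear model cannot be judged.

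Its precision is uncertain too. With N caregivers and 6 complete weeks, the within-person residual degrees of freedom are 6N − N − 2 = 5N − 2. The 95% half-width for a null correlation is tanh(1.96/√(5N − 3)). For assumed N of 10, 20 and 40 this gives 48, 98 and 198 degrees of freedom and half-widths of 0.28, 0.20 and 0.14. These figures also treat residuals as independent across a caregiver's weeks. They describe an optional extra in a study already reported in the past tense, serving an aim it does not state.

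**Conclusion.** The concern identifies loose wording and no analytic defect. The scope sentence can be read as promising three relationships, while the model provides two time trends. The sentence immediately after it limits the purpose to those two trends, and the model answers that purpose. No specified estimate, test or figure changes under either reading, so no change to the plan is called for. A narrower sentence would read better, but that is editorial.

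This rests on two points: the aim sentence governs the paragraph, and the generic outcome covers both steps and contact. Both are the natural reading, although the documents do not state either outright. The judgement would differ if a steps–contact association had been an intended result or if a conclusion about it had been drawn. The documents show neither.

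### Steps are measured in a Fitbit-only baseline week, but no stated analysis compares that week with the Go&Grow weeks; the linear week slope is not the change from baseline

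*Combined protocol and SAP*

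**What the plan says.** The study aims to evaluate "user experiences with Go&Grow and its impact on their well-being". Under Procedure & Data Collection, Session 1 gives the first Fitbit week a purpose: "Participants were asked to wear the Fitbit for the following week to assess their baseline physical activity level". Session 2 & Deployment Period then sets the order: "After one week of using the Fitbit, participants were trained on how to use Go&Grow", and "Caregivers were then asked to wear the Fitbit and use Go&Grow at least once every other day for 6 weeks".

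The Analysis section has two quantitative parts.

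- Paired t-tests, which ask whether "exercise self-efficacy and their management of distress scores changed significantly at posttest compared to the pretest". Steps are not included.
- A multilevel model to "determine whether participants increased in weekly average steps and weekly social contact over the 6-week intervention". The level 1 description reads "Weekly steps at level 1 were expressed as a wp intercept, week & wp error term", and level 2 reads "For level 2, wp intercept was expressed as a function of fixed intercept".

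The steps model therefore has a random intercept and a single fixed linear effect of week. It has no baseline-versus-Go&Grow term and no baseline covariate. The coding of week, and whether the Fitbit-only week enters the model, are not stated. The reference to the six-week intervention makes weeks 1–6 the likelier reading.

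**The concern.** The baseline week is the only measurement of steps before exposure to Go&Grow, and no stated comparison uses it. A linear slope over the Go&Grow weeks shows whether steps were rising or falling while the game was in use. It does not show whether they were higher than before. If the game lifts activity at once and the gain holds, the slope is flat. If the gain is large at first and partly wears off, the slope is negative. If steps dip and then recover to baseline, the slope is positive with no gain at all.

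Steps are not named as the well-being measure, but they are one of only two outcomes modelled weekly. A reader who takes the slope as the steps result could conclude that nothing happened, or that activity fell, when every week was above baseline. The opposite error is also possible.

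**Working it through.** The documents give no sample size, SD, effect size or power for steps, so there is no figure of the plan's to reproduce. The check has a part that follows from the design alone and a part that needs assumptions.

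**Design only.** Let μ(t) be the expected difference from baseline in steps/day in week t, with baseline as week 0 and μ(0) = 0.

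- Slope over weeks 1–6: Σ(t − 3.5)μ(t) / 17.5
- Slope over weeks 0–6: Σ(t − 3)μ(t) / 28
- Change from baseline: mean of μ(1) to μ(6)

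For a constant gain D, the weights t − 3.5 sum to zero over weeks 1–6, so the first slope is 0. Over weeks 0–6 the weights on weeks 1–6 sum to −2 − 1 + 0 + 1 + 2 + 3 = 3, so the slope is 3D/28 = 0.107 D per week.

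For a gain falling 1500, 1300, 1100, 900, 700, 500:

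- weeks 1–6: (−3750 − 1950 − 550 + 450 + 1050 + 1250)/17.5 = −3500/17.5 = −200
- weeks 0–6: (−3000 − 1300 + 0 + 900 + 1400 + 1500)/28 = −500/28 = −18

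| Profile over weeks 1–6 | Slope, weeks 1–6 | Slope, weeks 0–6 | Change from baseline |
|---|---|---|---|
| Sustained +1000 | 0 | +107 | +1000 |
| Fading +1500 to +500 | −200 | −18 | +1000 |
| Build-up 0 to +1500 | +300 | +268 | +750 |
| Drop of 500, recovering to 0 | +100 | +36 | −250 |
| Steady +100 per week from baseline | +100 | +100 | +350 |

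Under neither coding is the slope the change from baseline, and under both it can have the opposite sign.

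**Illustration under assumptions.** Assumed ranges: N 15–30, within-person weekly SD 1000–2500, between-person SD of the effect 0–1500; weeks independent within person, two-sided 5%. For the paired contrast, SE = √(effect SD² + SD² × 7/6)/√N. The factor 7/6 is 1 for the baseline week plus 1/6 for the mean of six weeks. Power comes from the noncentral t with N − 1 df. Figures for the slopes are simulated.

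Middle case, SD 1500, N 20, effect SD 0: SE = √(1500² × 7/6)/√20 = 362. The 95% CI half-width is 2.093 × 362 = 758, and power for a sustained +1000 is 74.5%. At effect SD 1000 and 1500, the half-widths are 891 and 1033 and the powers 60.6% and 48.5%.

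Probability of showing an increase when the gain is a sustained +1000:

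| Analysis | Middle case, effect SD 0/1000/1500 | Full assumed range |
|---|---|---|
| Slope, weeks 1–6 | 2–3% (chance) | 2–3% |
| Slope with baseline as week 0 | 38/36/33% | 13–85% |
| Paired contrast | 74.5/60.6/48.5% | 21–99.8% |

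Over the full range the half-width of the contrast runs from about 400 to 1700 steps. For the fading gain in the middle case, the weeks 1–6 slope is significantly negative in 68–70% of runs. For the build-up the order reverses: the slope detects it in 96%, the contrast in 50/39/30%.

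**Form of the contrast.** If caregivers respond differently, a fixed phase term with only a random intercept understates the uncertainty. With no mean effect, SD 1500 and N 20, its false-positive rate is 4.6/8.1/12.5% at effect SD 0/1000/1500, and it reaches 18.5% at SD 1000 with effect SD 1500. The paired t-test stays at 4.7–5.1% in every combination run at N 20. A model with a random phase effect, tested on N − 1 df, gives 2.8–4.8%.

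**The case against.** The strongest reply is that the model answers the question the plan sets: a trend over six weeks is what a linear week term tests. The plan never promises a comparison of steps with baseline, and a descriptive summary would also satisfy the stated purpose of the Fitbit week. That is right about the slope, which should stay. It does not supply an estimate of change from baseline.

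Second, the baseline week may have been coded as week 0, in which case it does enter the model. This cannot be ruled out, and that coding could detect a sustained rise. It does so inefficiently, its coefficient is still not the change from baseline, and the fading gain still has a negative slope.

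Third, which analysis has more power depends on the trajectory. For a steady rise of 200 steps per week from baseline (middle case, effect SD 0), the contrast has 45% power, the weeks 1–6 slope 69% and the week-0-coded slope 87%. This stands, and it is a reason to report both quantities.

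Fourth, the contrast leans on one week, the first week of tracker wear. Novelty may raise that week and incomplete wear may lower it. With no true effect, a 500-step error in it gives a false change in 8.5–69% of studies over the assumed range. There is also no control group. These limits stand and restrict what the contrast can support.

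**Conclusion.** The concern holds. A baseline week of steps is collected for a stated purpose, no stated analysis contrasts it with the Go&Grow weeks, and the week slope is a different quantity under either coding of week. That conclusion follows from the design. The powers, error rates and interval widths are illustrative and rest on assumed N, SD and effect variation. A flat or negative slope is compatible with a sustained gain, and a positive slope does not by itself show a rise above baseline. The existing model is not invalid. The gap should be fixed because it is real and cheap to close.

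**What to change.** - Add for steps a within-person contrast: each caregiver's mean over Go&Grow weeks 1–6 minus the baseline week, with a paired t-test and 95% CI. State how many caregivers and weeks contribute.
- If a mixed model is preferred, use a phase indicator with a person-level random phase effect, and centre week within the Go&Grow phase (week − 3.5 for weeks 1–6, 0 at baseline).
- Report the contrast beside the existing slope, state how week is coded and whether baseline is included, and limit claims from the slope to within-period trend.
- For social contact, no weekly measure before exposure is described, so report its slope only as a trend during the intervention.

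The cost is one extra estimate with its interval, from data already collected. The Analysis section is written in the past tense, so a contrast added after results are known must be labelled post hoc. The text should acknowledge the single, possibly biased baseline week and the lower power if effects vary between caregivers. The contrast supports a statement that steps changed from baseline; it does not support attributing the change to Go&Grow.
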